#### 1. INTRODUCTION

The purpose of this reporting and analysis plan (RAP) is to describe the analyses to be included in the Clinical Study Report for Protocol: 208135

#### 1.1. RAP Amendments

Revision chronology:

RAP Section	Amendment Details			
Reporting and Analysis Plan_Study208135_Final_V1 [16-JUL-2019]				
Reporting and Analysis Pl	an_Study208135_Amendment_Final_V1 [19-JAN-2020]			

 
Add boxplots for pharmacokinetic (PK) parameters overlaid with subjects categorized by elevated alanine aminotransferase (ALT) lev and categorized by progesterone level
 
				
9.1	Add adverse events of special interests			
9.2	Add plots of ALT, aspartate aminotransferase, alkaline phosphatase, total bilirubin, and gamma-glutamyl transferase by time			
9.3	Add liver events			
11.4.3	Add adverse events of special interest			
11.9.4	Add additional summary of treatment status and reasons for discontinuation from treatment			
11.9.5	
 
Add summary of adverse events of special interests
 
Add summaries of actual values for clinical chemistry, hematology, urine concentration, electrocardiograms (ECGs), and vital signs
 
Add summaries for liver events
 
			
11.9.6	Add figures of ALT, aspartate aminotransferase, alkaline phosphatase, total bilirubin, and gamma-glutamyl transferase by time			
11.9.8	
 
Add boxplots of ethinyl estradiol (EE), levonorgestrel (LNG), and GSK3640254 PK parameters against ALT
 
Add boxplots of EE, LNG, and GSK3640254 PK parameters against progesterone
 
			
11.9.11	Add listings of adverse events of special interests, vital results for subjects with liver stopping events, and subjects with liver monitoring/stopping event reporting			

# 2. SUMMARY OF KEY PROTOCOL INFORMATION

This is an open-label, single-sequence, one-way drug-drug interaction study to investigate the effect GSK3640254 has on the PK of a combination oral contraceptive containing EE and LNG. Effective contraception for women infected with human immunodeficiency virus (HIV) is important in the prevention of unplanned pregnancies.

# 2.1. Changes to the Protocol Defined Statistical Analysis Plan

Changes from the originally planned statistical analysis specified in the protocol are outlined in Table 1.

Table 1 Changes to Protocol Defined Analysis Plan

Protocol	Reporting & Analysis Plan		
Statistical Analysis Plan	Statistical Analysis Plan	Rationale for Changes	
Pharmacokinetic concentration population will be used for concentration listing.	Pharmacokinetic concentration population will be used for the PK concentration listings, summary tables, and plotting of concentration-time data.	Align with reporting and analysis plan (RAP) 209712 and RAP 208134.	
Pharmacokinetic parameter     population will be used for PK     parameter listing, summary     tables, and plotting of the     concentration-time data and PK     parameter summary	Pharmacokinetic parameter population will be used for PK parameter listings, summary tables, and statistical analysis tables.	Align with reporting and analysis plan (RAP) 209712 and RAP 208134.	

# 2.2. Study Objective(s) and Endpoint(s)

[figure not shown]
Objectives	Endpoints
Primary Objectives	Primary Endpoints
To assess the effect of GSK3640254 on the steady state PK of EE and LNG under fed conditions in healthy female participants	• AUC(0- $\tau$ ), Cmax, and C $\tau$ for EE and LNG
Secondary Objectives	Secondary Endpoints
To assess the effect of GSK3640254 on the PD of EE/LNG (suppression of ovulation as indicated by endogenous progesterone levels)	Serum progesterone levels
To assess the effect of GSK3640254 on LH and FSH	Serum FSH and LH levels
To characterize the steady state PK of GSK3640254 in the presence of EE/LNG	• AUC(0-τ), Cmax, Cτ, Tmax, and t1/2 for GSK3640254
To Characterize the steady state PK of EE/LNG alone and in the presence of GSK3640254	Tmax and t1/2 for EE and LNG
To assess the safety and tolerability of GSK3640254 and EE/LNG when given in combination in healthy female participants	Safety and tolerability parameters for AEs/SAEs, observed and change from baseline clinical laboratory assessments, ECGs, and vital sign measurements

AE = adverse event; AUC(0- $\tau$ ) = area under the plasma concentration-time curve from time 0 to the end of the dosing interval at steady state; Cmax = maximum observed concentration; C $\tau$  = Plasma concentration at the end of the dosing

Objectives	Endpoints

interval; ECG = electrocardiogram; EE = ethinyl estradiol; FSH = follicle-stimulating hormone; LH = luteinizing hormone; LNG = levonorgestrel; PD = pharmacodynamic; PK = pharmacokinetic; SAE = serious adverse event; t1/2 = apparent terminal phase half-life; Tmax = time of maximum observed concentration.

#### 2.3. Study Design

 The "Washout" period of this study should be called "Follow Up" as there is only one treatment period. See 208135 Protocol Clarification dated 10-June-2019

# 2.4. Statistical Hypotheses

The hypothesis tested by this study:

H0:  $\mu_{test}/\mu_{ref} < 0.8$  or  $\mu_{test}/\mu_{ref} > 1.25$ 

 $H_a: 0.8 \le \mu_{test}/\mu_{ref} \le 1.25$ 

Where  $\mu_{test}$  is the geometric least-squares mean for PK parameters of EE/LNG when coadministered with GSK3640254 and  $\mu_{ref}$  is the geometric least-squares mean for PK parameters of EE/LNG when administered alone. If the null hypothesis is not rejected, then there is sufficient evidence to suggest an effect of GSK3640254 on the PK of EE/LNG; however, if the null hypothesis is rejected, then there is no evidence to suggest an effect of GSK3640254 on the PK of EE/LNG. The hypothesis test will be assessed using Schuirmann's 2 one-sided t-test procedure with  $\alpha$ =0.05 for each test (Schuirmann, 1987). Each ratio will be compared to 0.8 and 1.25 as described above. Lack of effect is to be demonstrated if the 90% CIs for both LNG and EE lie within 0.8 and 1.25.

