#### **Model Specification**

- Analyses will be performed on the natural logarithms of AUC(0-τ), Cτ and Cmax using linear mixed-effect models with treatment as a fixed effect, participants as random effect, and measurements within participant as repeated measures.
- Effects will be estimated, and confidence intervals (CIs) will be constructed for the following treatment comparisons:
  - Treatment B versus Treatment A
- Point estimates and 90% CIs for treatment differences on the log scale derived from the model will be exponentiated to obtain estimates for geometric mean ratios and CIs on the original scale.

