#### **Model Results Presentation**

- Statistical analysis by analysis of variance (ANOVA) will be presented in tabular format with geometric mean ratios for:
  - Treatment B versus Treatment A

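### SAP Section 2.4 treats failure to show equivalence as evidence of an interaction, so an imprecise 90% CI containing 1.0 would be reported as an effect

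*SAP*

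**What the plan says.** Section 2.4 of the SAP defines H0 as a test-to-reference ratio below 0.8 or above 1.25, and Ha as a ratio within those limits. On the method: "The hypothesis test will be assessed using Schuirmann's 2 one-sided t-test procedure", with alpha 0.05 for each one-sided test.

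It then gives two readings of the result:

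- Non-rejection: "If the null hypothesis is not rejected, then there is sufficient evidence to suggest an effect of GSK3640254 on the PK of EE/LNG".
- Rejection: "if the null hypothesis is rejected, then there is no evidence to suggest an effect of GSK3640254 on the PK of EE/LNG".

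The section closes with a decision rule: "Lack of effect is to be demonstrated if the 90% CIs for both LNG and EE lie within 0.8 and 1.25".

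These readings serve the primary objective in Section 2.2: "To assess the effect of GSK3640254 on the steady state PK of EE and LNG under fed conditions in healthy female participants".

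Section 7.1.4.1 plans the estimates without any verdict wording. Under Model Specification: "Point estimates and 90% CIs for treatment differences on the log scale derived from the model will be exponentiated". Under Model Results Presentation, geometric mean ratios for Treatment B versus Treatment A are to be tabulated.

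**The concern.** In an equivalence test the burden of proof lies on showing equivalence. When H0 is not rejected, either the ratio has really moved or the data are too imprecise to tell. Section 2.4 assigns every such result to the first explanation, so absence of proof of equivalence becomes proof of an interaction. Nowhere else does the SAP allow an inconclusive outcome or correct the sentence.

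At stake is the written conclusion on the primary objective. Followed literally, the report could state that there is evidence of an interaction with an oral contraceptive on the strength of an interval that contains 1.0.

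The rejection sentence has a milder form of the same looseness. A narrow CI can lie inside 0.80 to 1.25 and still exclude 1.0. That shows a small change within the bounds, not an absence of evidence for any change.

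**Working it through.** **Inputs from the SAP.** Bounds 0.80 and 1.25, alpha 0.05 per one-sided test and a 90% CI (Section 2.4); log-scale analysis with exponentiated results (Section 7.1.4.1); a within-participant comparison of B with A.

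**Assumed inputs.** The SAP gives no sample size, within-subject CV (CVw) or expected ratio. The illustrations use n = 16 and 20 with CVw from 15% to 30%, for one ratio with complete pairs.

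**The plan's own figure.** Two one-sided tests at 0.05 correspond to a CI of level 1 − 2 × 0.05 = 0.90. The log bounds are ln 0.80 = −0.2231 and ln 1.25 = +0.2231. Test and interval agree.

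**Formula.** With complete pairs:

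- within-subject log variance: s² = ln(1 + CVw²)
- standard error: SE = √(2s²/n)
- half-width: h = t(0.95, n−1) × SE
- 90% CI: observed ratio × exp(±h)

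**Failed test, CI contains 1.0.** n=16, CVw 30%, ratio 0.95:

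- s² = ln(1.09) = 0.0862
- SE = √(2 × 0.0862/16) = 0.1038
- h = 1.753 × 0.1038 = 0.182
- CI = 0.95 × (0.834, 1.200) = 0.792 to 1.140

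Likewise n=16, CVw 25%, ratio 0.92 gives 0.790 to 1.072. Section 2.4 would call both results evidence of an effect.

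**Passed test, CI excludes 1.0.** n=20, CVw 15%, ratio 0.90: SE = 0.0472, h = 1.729 × 0.0472 = 0.0816, CI = 0.830 to 0.976. H0 is rejected although the interval shows a decrease.

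**How often, with a true ratio of 1.00.** The probabilities come from integrating over the chi-square distribution of the variance estimate and were confirmed with 1,000,000 simulated trials per setting.

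| n | CVw | CI inside bounds | Crosses a bound, contains 1.0 | Crosses a bound, excludes 1.0 |
|---|---|---|---|---|
| 16 | 15% | 98.3% | 0.34% | 1.4% |
| 16 | 20% | 83.7% | 9.6% | 6.7% |
| 16 | 25% | 57.7% | 33.0% | 9.3% |
| 16 | 30% | 32.8% | 57.3% | 9.9% |
| 20 | 15% | 99.6% | 0.01% | 0.35% |
| 20 | 20% | 92.6% | 2.7% | 4.7% |
| 20 | 25% | 73.6% | 17.7% | 8.7% |
| 20 | 30% | 49.9% | 40.3% | 9.8% |

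A CI wholly outside the bounds occurs in at most 0.02% of trials in these settings. Only the column for intervals that contain 1.0 measures the concern.

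**Why a simple pass-or-inconclusive split is not enough.** n=16, CVw 20%, observed ratio 0.75: SE = 0.0700, h = 0.1227, CI = 0.663 to 0.848. This crosses 0.80 but plainly shows a decrease. With a true ratio of 0.75 in that setting, about 76% of intervals cross a bound and exclude 1.0, 22% lie wholly outside the bounds, 0.9% cross a bound and contain 1.0, and 0.6% lie inside.

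**The case against.** The strongest reply is that little depends on the sentence. Section 2.4 ends with a correct rule, the planned tables show ratios and 90% CIs without a verdict, and any reader can see a wide interval. The faulty sentence cannot produce a false claim of no interaction, because the closing rule governs that claim. All of this is right, and it confines the fault to wording. But the closing rule says only when lack of effect is shown. The sentence at issue is the only text that says what to conclude otherwise, and it is wrong.

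Second, the high rates belong to weak designs. At CVw 30% a single ratio passes in only about 33% (n=16) or 50% (n=20) of trials even with no effect. Where single-ratio power exceeds 80%, at CVw 20%, the rates are 9.6% and 2.7%. This stands. The figures also cover one ratio, whereas the plan tests three parameters for each of two analytes, six in all. They are not an estimate for this study.

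Third, the rejection clause can be read as shorthand for no effect beyond the bounds, since the hypotheses define effect that way. That is a fair reading and makes this part minor. It does not rescue the non-rejection clause.

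Fourth, the fix could be a single clause. That would cure the error, but it would leave a CI such as 0.663 to 0.848 without a defined description.

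**Conclusion.** The concern holds. Section 2.4 states a wrong inference for the primary conclusion, and nothing elsewhere in the SAP corrects it. The logic fails at any sample size and CV. How often it would mislead depends on values the SAP does not give: under the assumed settings and a true ratio of 1.00, from 0.01% (n=20, CVw 15%) to about 57% (n=16, CVw 30%) of trials for one ratio. It is negligible when precision is good and common when it is poor. No estimate, interval, error rate or planned display is affected. It should be corrected because the pre-specified conclusion could contradict the interval printed beside it.

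**What to change.** Keep the test, alpha, bounds, model and the closing rule with its joint EE and LNG requirement. Replace the non-rejection sentence with wording such as:

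> When H0 is not rejected for a ratio, lack of effect has not been demonstrated for that ratio, and interpretation rests on its geometric mean ratio and 90% CI. An effect beyond the bounds is concluded only if the 90% CI lies wholly below 0.80 or wholly above 1.25. A CI that crosses a bound but excludes 1.0 is described as a change whose size relative to the bounds is unresolved. A CI that crosses a bound and contains 1.0 is inconclusive.

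In the rejection sentence, say that there is no effect beyond the 0.80 to 1.25 bounds. Applying the wording to each ratio covers the case where the six ratios fall into different classes.

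The cost is a text edit. The ratios and 90% CIs are already planned, so no new data, analysis or display is needed. If the sentence was carried over from the protocol, add one entry to Table 1 in Section 2.1.

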#### **Endpoint / Variables**

• Plasma primary PK endpoints include AUC(0- $\tau$ ), C $\tau$ , and Cmax for EE and LNG (Treatments A and B), as data permit

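### Section 2.4 reads rejection of the non-equivalence null as no evidence of an effect, when rejection shows only that any effect lies within 0.80-1.25

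*SAP*

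**What the plan says.** Section 2.4 puts the test-to-reference ratio of geometric means below 0.8 or above 1.25 under the null and between those limits under the alternative. It uses Schuirmann's two one-sided tests with alpha "0.05 for each test", and adds that "Each ratio will be compared to 0.8 and 1.25 as described above".

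Two interpretations are then fixed in advance. On non-rejection: "If the null hypothesis is not rejected, then there is sufficient evidence to suggest an effect of GSK3640254 on the PK of EE/LNG". On rejection: "if the null hypothesis is rejected, then there is no evidence to suggest an effect of GSK3640254 on the PK of EE/LNG". The section closes with: "Lack of effect is to be demonstrated if the 90% CIs for both LNG and EE lie within 0.8 and 1.25".

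Section 7.1.4.1 supplies the estimates. The endpoints are AUC(0-τ), Cτ and Cmax "for EE and LNG (Treatments A and B), as data permit", and under Model Specification "Point estimates and 90% CIs for treatment differences on the log scale derived from the model will be exponentiated" to give geometric mean ratios. Tables 3.13 and 3.14 carry the EE and LNG analyses.

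**The concern.** The test compares the ratio with 0.80 and 1.25 and never with 1. Its rejection therefore licenses a statement about containment within the bounds. The SAP attaches a statement about the absence of evidence for any effect, which is a different claim and can be false when the test rejects. A CI that sits inside the bounds and wholly below 1 is good evidence of a reduction, and equally good evidence that the reduction is smaller than 20%. The rejection clause acknowledges only the second part, and describes it as no evidence.

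The clause governs the favourable outcome of the primary analysis. The primary objective is the effect of GSK3640254 on EE and LNG exposure, and Section 2 gives effective contraception as the reason for the question. An error here leans towards reassurance about contraceptive exposure, and the conclusion could disagree with the ratio and CI printed in Tables 3.13 and 3.14.

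**Working it through.** **1. The plan's own pairing of test and interval.** Two one-sided tests at 0.05 each correspond to a CI of level 1 − 2 × 0.05 = 0.90. The 90% CI in Section 2.4 is therefore right. The test and the decision rule are sound.

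**2. A case in which the test rejects and the CI excludes 1.** From the SAP: bounds 0.80 and 1.25, alpha 0.05 per test, analysis on the log scale. Assumed, because the SAP does not give them: 20 complete pairs, within-participant CV 12%, observed ratio 0.875. A paired analysis stands in for the mixed model.

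- Within-participant SD on the log scale: √ln(1 + 0.12²) = 0.1196
- Standard error of the log ratio: 0.1196 × √(2/20) = 0.0378
- t(0.95, 19 df) = 1.729
- 90% CI: 0.875 × exp(±1.729 × 0.0378) = 0.820 to 0.934
- Against 0.80: t = ln(0.875/0.80)/0.0378 = 2.37, one-sided p = 0.014
- Against 1.25: t = −9.43, one-sided p below 0.00001
- Against 1: t = ln(0.875)/0.0378 = −3.53, two-sided p = 0.0022

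Both one-sided tests reject, so Section 2.4 concludes that there is no evidence of an effect. The same data give strong evidence of a reduction of about 12.5%.

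The result does not hinge on these inputs. A 90% CI of exactly 0.82-0.93 has a ratio of √(0.82 × 0.93) = 0.873. Over 9 degrees of freedom up to the normal limit, p against 0.80 runs from 0.016 to 0.011, and two-sided p against 1 from 0.0034 to 0.0004.

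**3. How often this could happen.** Paired log ratios were simulated (400,000 runs per setting), counting runs whose 90% CI lay inside 0.80-1.25 and excluded 1. N, CV and true ratio are all assumptions. Each range covers true ratios of 0.88 and 0.90, for one parameter.

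| Pairs | CV | P(inside bounds and excludes 1) | Share of rejections whose CI excludes 1 |
|---|---|---|---|
| 20 | 10% | 0.89-0.92 | 94-99% |
| 20 | 15% | 0.45-0.47 | 61-73% |
| 20 | 20% | 0.12 | 21-27% |
| 20 | 25% | 0.02 | 4-5% |
| 12 | 10% | 0.61-0.64 | 75-86% |
| 12 | 15% | 0.14-0.15 | 26-33% |
| 12 | 20% | 0.02 | 6-8% |
| 12 | 25% | below 0.01 | about 2% |

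The third column is the one to use for how often the conflict would arise. The fourth is conditional on rejection and is always larger.

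**The case against.** The strongest reply is that the paragraph defines its own term. Section 2.4 sets the hypotheses by the bounds, compares each ratio only with the bounds, and ties its closing sentence to them. On that reading, effect is shorthand for an effect beyond 0.80-1.25. This is probably what was meant, but no qualifier appears in Section 2.4 or anywhere else in the SAP, and the clause is worded as a statement about evidence. The shorthand should be spelled out.

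Four further points stand and limit the finding:

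- **The estimate is not hidden.** The ratio and 90% CI are required by Section 7.1.4.1. A reader might infer that a fall in exposure would go unreported; the SAP does not support that.
- **One CI does not earn the overall label.** The closing sentence needs the CIs for both EE and LNG inside the bounds, and Section 7.1.4.1 lists three parameters for each. The worked case assumes that the other CIs are inside too, and the simulation covers one parameter, not the joint event.
- **The frequency rests on assumed inputs.** It runs from negligible to common across plausible CVs.
- **Flagging every in-bounds CI that excludes 1 would be a poor remedy.** It would amount to a test against 1 at the 10% level on six ratios. If all true ratios were 1 and the six were independent, with almost all CIs inside the bounds, 1 − 0.9⁶ = 47% of such studies would flag at least one (fewer with correlation).

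**Conclusion.** The rejection clause is wrong as written, and the closing sentence repeats the error in shorter form. Rejecting the null shows that any effect on that parameter lies within 0.80-1.25 and nothing more. The fault is confined to the prespecified conclusion: the hypotheses, bounds, alpha, model, CI and displays need no change.

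A reader might go further and infer that the equivalence test is the wrong analysis, or that this trial will probably report a real reduction as none. Neither follows. The test is correct, and the SAP gives neither the sample size nor the CV needed to say how likely the conflict is. The logical error does not depend on those figures; its practical weight does. It is worth correcting because it governs the primary conclusion and the correction is cheap.

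The non-rejection half of the same sentence has the mirror fault. A merely imprecise CI of 0.78-1.28 has a ratio of √(0.78 × 1.28) = 1.00 and a two-sided p against 1 above 0.99. It fails to reject (one-sided p about 0.07 on each side) and would be called sufficient evidence of an effect.

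**What to change.** In Section 2.4:

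1. Replace the rejection clause with: *if the null hypothesis is rejected, any effect of GSK3640254 on that PK parameter of EE/LNG is concluded to lie within 0.80-1.25, and is to be interpreted with the geometric mean ratio and 90% CI.*
2. In the closing sentence, replace the opening three words with: *Lack of an effect outside 0.80-1.25*.
3. In the same edit, reword the non-rejection half, for example: *if the null hypothesis is not rejected, an effect outside 0.80-1.25 has not been excluded; this alone does not show that an effect exists.*

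Do not add a rule that labels every in-bounds CI excluding 1 as an increase or decrease.

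The cost is a few lines of text, with no change to the analysis or displays, and a slightly less absolute headline. Section 2.4 sits under the summary of key protocol information, so the wording may originate in the protocol, which is not at hand. If it does, record the change in Table 1 of Section 2.1.

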### 3. PLANNED ANALYSES

# 3.1. Final Analyses

The final planned primary analyses will be performed after the completion of the following sequential steps:

- 1. All participants have completed the study as defined in the protocol.
- 2. All required database cleaning activities have been completed and final database release (DBR) and database freeze (DBF) have been declared by Data Management.

### 4. ANALYSIS POPULATIONS

Population	Definition / Criteria	Analyses Evaluated
Screened	
 
All participants who signed the informed consent form
 
This population will be used for screen failure listing and summary
 
	Study Population
Safety	
 
All participants who received at least 1 dose of study medication.
 
This population will be used for all demographic, disposition (exclude screen failure), and safety listings, summaries, and figure
 
	

Study Population

Safety

Pharmacokinetic Concentration	
 
All participants who underwent plasma PK sampling and had evaluable PK assay results.
 
This population will be used for the PK concentration listings, summary tables, and plotting of concentration-time data.
 
	PK Concentration
Pharmacokinetic Parameter	
 
All participants who underwent plasma PK sampling and had evaluable PK parameters estimated.
 
This population will be used for PK parameter listings, summary tables, and statistical analysis tables.
 
	

PK Parameter

PK statistical analysis

Pharmacodynamic Concentration	
 
All participants who underwent plasma PD sampling and had evaluable PD assay results.
 
This population will be used for the PD concentration listings, summary tables, and figures.
 
	PD Concentration

Refer to Appendix 9: List of Data Displays which details the population used for each display.

